10.2 Patient demographics/other baseline characteristics

Demographic and other baseline data (including disease characteristics) will be listed and summarized by patients groups formed by the type of cancer at study entry using the FAS (please see [Table 4-1 of Appendix B](#) for predicted target cancer population). Additional groups may be added based on enrollment (See [Appendix R](#)). Categorical data, such as gender, race, etc., will be presented by frequencies and percentages. Descriptive summary statistics (e.g., frequency, mean, median, range and standard deviation) will be used to present numeric data.

10.3 Treatments (study treatment, concomitant therapies, compliance)

10.3.1 Study medication

Duration of study treatment exposure, cumulative dose and dose intensity will be summarized by the patient groups as above using the Safety Set. The number of patients with dose changes/interruptions will be presented along with reasons for the dose change/interruption. The Safety Set will be used for the tables and listings.

10.3.2 Concomitant therapies

Concomitant medications and significant non-drug therapies taken concurrently with the study drugs will be listed and summarized for the FAS by Anatomical Therapeutic Chemical Classification System (ATC) term and preferred term by means of frequency counts and percentages. These summaries will include medications starting on or after the start of study

treatment (defined as cycle 1 day 1) or medications starting prior to the start of study treatment and continuing after the start of study treatment.

Any prior concomitant medications or significant non-drug therapies starting and ending prior to the start of study treatment will be listed. The Safety Set will be used for all above mentioned concomitant medication tables and listings.

10.4 Primary objective

The primary endpoint is clinical benefit rate (CBR) in each group, with clinical benefit being assessed at 16 weeks.

For patients with solid tumors the assessment criteria will be RECIST 1.1 and will include responses of CR or PR or SD \geq 16 weeks. For hematologic tumors other appropriate hematological response criteria will apply and are included in the appendices.

For patients with TIO diagnosis without measurable/evaluable disease, the following criteria will be the assessment at 16 weeks:

- the tumor associated changes of metabolic parameters: plasma level of FGF23 < or =180 RU/mL; and inorganic phosphorous, calcium, and 1-25-dihydroxy vitamin D greater than the LLN (- 20%); and
- without requirement of supplementation therapy for at least the preceding cycle of the 16 week assessment.

For solid tumors, an assessment of CR or PR must be confirmed at least 4 weeks after initial observation, using RECIST 1.1. If the two assessments differ, the best response will be determined by [Table 3-3](#) of [Appendix A](#).

10.4.1 Variable

The primary efficacy variable is the clinical benefit rate (CBR) (e.g. defined as CR or PR or SD \geq 16 weeks for solid tumors) at week 16.

10.4.2 Statistical hypothesis, model, and method of analysis

The study will enroll patients from at least 6 histologic groups. In addition, another group simply referred to as “Other” may be identified and enrolled throughout the study.

Let Y_i be the response indicator for the i^{th} subject, and let R_g be the assumed probability of response within a control population and $\pi_g = \Pr(Y_i = 1 | g_i = g)$ be the underlying probability of response for group g . We transform to the logit scale for modeling purposes. Let θ_g be the mean log odds treatment effect, i.e.:

$$\theta_g = \log\left(\frac{\pi_g}{1 - \pi_g}\right) - \log\left(\frac{R_g}{1 - R_g}\right) \theta_g = \log\left(\frac{\pi_g}{1 - \pi_g}\right) - \log\left(\frac{R_g}{1 - R_g}\right)$$

Thus, θ_g is the group specific logistic regression coefficient for the treatment within group g . The primary analysis is a set of group specific tests that $\theta_g > 0$, meaning that the treatment is better than the assumed control rate within that group. Thus, we wish to test the set of hypotheses

$$H_{0g} : \theta_g \leq 0$$

$$H_{1g} : \theta_g > 0$$

We proceed in a Bayesian fashion, assigning a prior distribution (details in [Appendix R](#)) and computing the posterior probability of H_{1g} within each group g . If, at the final analysis,

$$\Pr(\theta_g > 0 \mid \text{data}) > 0.90$$

Then group g will be declared a success (thus, the final analysis produces a separate decision for each group). The trial also allows for early stopping of groups, described below.

The statistical design borrows information across subgroups with a hierarchical model. The hierarchical model allows dynamic borrowing of information between groups such that more borrowing occurs when the groups are consistent and less borrowing occurs when the groups differ. In this way, the model is a compromise between the two alternate extremes of either a completely pooled analysis or a separate analysis in each group. We additionally incorporate a clustering mechanism that allows borrowing within clusters but treats clusters separately. This minimizes borrowing across groups that are quite different in terms of CBR.

The purpose of such an analysis (discussed in more detail in the appendix) is to produce higher power or lower type I error in situations where we see some commonality (identical effects are not required) among the groups. The model will borrow more in situations where the groups appear similar than situations where the groups appear different.

Details of the hierarchical model are provided in [Appendix R](#).

10.4.3 Evaluation of trial success and futility

The clinical benefit rate will be evaluated for futility and early success by comparing posterior quantities for the rate to pre-specified early stopping criteria. The evaluations are planned to occur after the first 30 patients have been dosed for at least 16 weeks or discontinued, then every 13 weeks thereafter.

Early futility

If there is less than 10% probability that the response rate in a group exceeds the historical rate R_g , then the group will stop enrollment early for futility. Formally, enrollment will stop early for futility if:

$$\Pr(\pi_g > R_g) < 0.10.$$

A group is only eligible for early stopping once a minimum of 10 patients has been evaluated for response in that group.

Early success

If there is at least 95% probability that the response rate in a group exceeds the historical rate, then the group will stop enrollment early for success. Formally, enrollment will stop early for success if:

$$\Pr(\pi_g > R_g) > 0.95.$$

A minimum of 15 subjects will need to be evaluated prior to declaring a group to be efficacious.

Final analysis

The final analysis will occur when both accrual and follow-up are complete for all subjects. If, at the completion of the trial, there is at least 90% probability that the response rate in a group exceeds the historical rate, then the group will be considered a success. Formally:

$$\Pr(\pi_g > R_g) > 0.90.$$

In addition, a group will be considered as “promising” if:

$$0.80 = \Pr(\pi_g > R_g) < 0.90.$$

The control rates R_g are shown in [Table 14-1 of Appendix R](#).

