9.4 Database management and quality control

This study will be using eCRFs and the designated CRO will review the data entered by investigational staff for completeness and accuracy. Electronic data queries stating the nature of the problem and requesting clarification will be created for discrepancies and missing values and sent to the investigational site via the EDC system. Designated investigator site staff are required to respond promptly to queries and to make any necessary changes to the data.

Concomitant treatments and prior medications entered into the database will be coded using the WHO Drug Reference List, which employs the Anatomical Therapeutic Chemical classification system. Medical history/current medical conditions and adverse events will be coded using the Medical dictionary for regulatory activities (MedDRA current version) terminology.

Data from the screening molecular analysis will be collected locally and entered directly onto the eCRF. Tissue samples for pathway activation confirmation will be analyzed centrally.

At the conclusion of the study, the occurrence of any protocol deviations will be determined. After this action has been completed and the data has been verified to be complete and accurate, the database will be declared locked and the data made available for data analysis. Authorization is required prior to making any database changes to locked data, by joint written agreement between the US Oncology Medical Affairs Franchise Head and the US Oncology Medical Affairs Franchise Vice President.

After database lock, the investigator will receive a CD-ROM or paper copies of the patient data for archiving at the investigational site.

10 Statistical methods and data analysis

All data except the primary efficacy variable clinical benefit rate will be analyzed by a designated CRO in collaboration with Novartis. The analysis of the clinical benefit rate will be performed by a separate CRO using the Bayesian adaptive design approach described in details in [Appendix R](#). Any data analysis carried out independently by the investigator should be submitted to Novartis before publication or presentation. The data from all centers that participate in this study will be combined in the final safety and efficacy analysis.

This trial will enroll patients from at 6 histologic groups:

- NSCLC - Squamous
- Ovarian
- Glioblastoma Multiforme
- Squamous Head and Neck
- Bladder
- Cholangiocarcinoma

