In addition, another group currently simply referred to as “Other” may be identified and enrolled throughout the study (e.g. “Other” will be a focused histologic group, but may not be explicitly identified until the trial is ongoing due to recruitment issues). We discuss the logistics in more detail below, but a decision will only be made for a group other than the 6 listed if 1) more than 3 patients are enrolled in the group, and 2) a reasonable estimate of the clinical benefit rate is available.

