14.1.1.0 Introduction

This document outlines the adaptive design framework to be used for this study and all modules.

Although the selected tumor types may vary by trial, this document outlines the design and analysis approach based on 8 example tumor cohorts:

- Lung NSCL
- Bladder
- Breast
- Colorectal
- GIST
- HNSCC
- Ovarian
- Sarcoma

Other tumor types may be considered for trials if 1) 4 or more patients are enrolled in the cohort, and 2) a reasonable estimate of the clinical benefit rate is available.

The primary endpoint is clinical benefit rate (CBR) in each cohort, with clinical benefit being assessed at 16 weeks. All patients will receive the experimental treatment for that particular trial.

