14.1.1.2 Trial logistics

Each trial will enroll all available subjects in all cohorts for 2 years unless a cohort cap is reached, or a cohort is stopped early, or the trial is stopped early by Novartis. Each trial will enroll no more than 30 evaluable subjects in each cohort. Interim monitoring will be conducted starting after the first 30 patients are enrolled overall (across all cohorts), and continuing each 13 weeks thereafter till study enrollment closure. After that, one CBR analysis will be done after database lock. At each interim data review, response information for the various cohorts will be evaluated to determine the current $\Pr(\theta_g > 0 | \text{data})$ within each cohort, with sufficiently high/low values used to stop the cohort for success/futility. A minimum of 10 patients will be required in a cohort before it may discontinue enrollment for futility, and a minimum of 15 patients are required before discontinuing a cohort for efficacy. If a cohort stops enrolling early, the remaining cohorts will continue until the end of 2 years or until the other cohorts reach their own early stopping criteria. The final analysis will occur after the database lock for the primary CSR.

Each trial will enroll subjects in all listed cohorts. In addition, should other cohorts be identified throughout the trial, the following mechanism will be used. If another cohort is identified, it will not be placed into the statistical analysis unless 3 subjects enroll within the cohort (thus, the trial may enroll multiple additional cohorts, but a cohort will only be added to the list if at least 3 patients enroll from that cohort). Thus, it is possible (but not viewed as likely) that multiple additional cohorts may be added to the trial if the trial has sufficient enrollment in multiple additional cohorts. In addition to sufficient enrollment, the sponsor must have a reasonable estimate of the control clinical benefit rate.

Subjects within any cohort which does not reach the minimum enrollment will be excluded from the interim and final analyses. As the study continues, early interim data reviews may be based on fewer cohorts than later interim data reviews, as the interim data reviews will include whatever cohorts have satisfied the criteria at the time of the data review.

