14.4.4.1 Assumptions

Accrual – Two scenarios for the assumed two-year expected accrual are investigated: 1) 10 subjects per group and 2) 5 subjects per group. Note that these are averages, the actual number

of available patients is simulated as a Poisson distribution with the specified mean. Also note that the group cap of 30 applies, and thus if the number of available patients in a group exceeds 30, only the first 30 available patients in that group will be enrolled in the study.

Dropouts – We assume no dropouts for the purpose of this simulation.

Control Rates – [Table 14-1](#) shows the assumed control clinical benefit rates for each group.

Table 14-1 Assumed control CBR values used in the simulations

Tumor Type	Assumed Control Rate (Rg)
Lung LSCL	0.45
Bladder	0.47
Breast	0.50
Colorectal	0.38
GIST	0.50
HNSCC	0.45
Ovarian	0.47
Sarcoma	0.40

We consider four possible scenarios, or possible “truths” in the simulation. These consisted of a null scenario (where the treatment has no effect for any group), an alternative scenario (where the treatment is effective in all groups), a scenario where the treatment was effective in two of the groups, and a scenario where the treatment was effective in half of the groups.

Treatment Rates - The treatment rates for each scenario are shown in the table below. Values identical to the control are shown in red, while values greater than the assumed control rate are shown in green.

	Null	Alternative	Two	Half
Lung LSCL	0.45	0.71	0.45	0.45
Bladder	0.47	0.73	0.47	0.47
Breast	0.50	0.75	0.50	0.50
Colorectal	0.38	0.65	0.38	0.38
GIST	0.50	0.75	0.50	0.75
HNSCC	0.45	0.71	0.45	0.71
Ovarian	0.47	0.73	0.73	0.73
Sarcoma	0.40	0.67	0.67	0.67

Simulation Details – For each scenario we simulated 1000 trials. For each interim within each trial, we ran 50,000 MCMC iterations after a 1,000 MCMC iteration burnin.

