6.1 Clinical Benefit Rate (CBR)

Clinical benefit is determined by investigator assessment for each tumor assessment and is defined as responses of CR or PR or SD \geq 16 weeks. For subjects with TIO diagnosis without measureable/evaluable disease, the following criteria will be used to determine the assessment at 16 weeks:

- the tumor associated changes of metabolic parameters: plasma level of FGF23 < or =180 RU/mL; and inorganic phosphorous, calcium, and 1-25-dihydroxy vitamin D greater than the lower limit of normal (LLN) (20%); and
- without requirement of supplementation therapy for at least the preceding cycle of the 16 week assessment.

Subjects with TIO diagnosis, but having known underlying tumor/disease type, their tumor response summaries will be treated same as for subjects with the same underlying tumor type.

In addition to tumor-specific measurements (e.g., radiological assessment of tumor response for solid tumors), progressive disease will also be considered when it was indicated either as a reason based on clinical assessment for the study treatment discontinuation or as a cause of on-treatment death. CR and PR (for solid tumors) require a confirmation that is at least a minimum of 4 weeks after the initial observation of response. Subjects who had confirmed CR/PR or SD prior to 16 weeks, but discontinued prior to 16 weeks for reasons other than

progressive disease, will have their clinical benefit defined as non-evaluable; subjects who had confirmed CR/PR or SD prior to 16 weeks, but progressed prior to 16 weeks, will be considered as not achieving clinical benefit; subjects who had CR/PR/SD occurred prior to 16 weeks, but progressed at or after 16 weeks without evidence of CR/PR/SD at or after 16 weeks, will also be considered as not achieving clinical benefit. CBR will be analyzed by comparing achieved CBR with a historical control rate of each tumor type, and if there is at least 90% probability that the response rate in a tumor type exceeds the historical rate, then the tumor type will be considered a success; it will be considered as promising if the probability is between 80% and 90%. Details for the analyses of CBR are located in Section [Error! Reference source not found.](#)

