10.4.1 Assumptions

Accrual – Two scenarios for the assumed two-year expected accrual are investigated: 1) 10 subjects per group and 2) 5 subjects per group. Note that these are averages, the actual number of available subjects is simulated as a Poisson distribution with the specified mean.

Also note that the group cap of 30 applies, and thus if the number of available subjects in a group exceeds 30, only the first 30 available subjects in that group will be enrolled in the study.

Dropouts – We assume no dropouts for the purpose of this simulation.

Control Rates – Table 1 shows the assumed control clinical benefit rates for each group.

Table 1 – Controlled CBR values used in the simulations	
Tumor Type	Assumed Control Rate (R_g)
Lung LSCL	0.45
Bladder	0.47
Breast	0.50
Colorectal	0.38
GIST	0.50
HNSCC	0.45
Ovarian	0.47
Sarcoma	0.40

We consider four possible scenarios, or possible “truths” in the simulation. These consisted of a null scenario (where the treatment has no effect for any group), an alternative scenario (where the treatment is effective in all groups), a scenario where the treatment was effective in two of the groups, and a scenario where the treatment was effective in half of the groups.

Treatment Rates - The treatment rates for each scenario are shown in the table below. Values identical to the control are shown in normal text, while values greater than the assumed control rate are shown in bold.

	Null	Alternative	Two	Half
Lung LSCL	0.45	0.71	0.45	0.45
Bladder	0.47	0.73	0.47	0.47
Breast	0.50	0.75	0.50	0.50
Colorectal	0.38	0.65	0.38	0.38
GIST	0.50	0.75	0.50	0.75
HNSCC	0.45	0.71	0.45	0.71
Ovarian	0.47	0.73	0.73	0.73
Sarcoma	0.40	0.67	0.67	0.67

Simulation Details – For each scenario we simulated 1000 trials. For each interim within each trial, we ran 50,000 MCMC iterations after a 1,000 MCMC iteration burnin.

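### No control rate R_g is stated for glioblastoma or cholangiocarcinoma, so the primary decision for two of the six cohorts cannot be computed from the plan

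*Protocol*

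**What the plan says.** Protocol Section 10 opens with "This trial will enroll patients from at 6 histologic groups": squamous NSCLC, ovarian, glioblastoma multiforme, squamous head and neck, bladder and cholangiocarcinoma. Section 10.4.3 sets the limits on Pr(π_g > R_g): below 0.10 for futility, above 0.95 for early success, above 0.90 for final success, and 0.80 to 0.90 for promising. On the null value it says "The control rates R_g are shown in" Table 14-1 of Appendix R. SAP 6.1 agrees: "CBR will be analyzed by comparing achieved CBR with a historical control rate of each tumor type".

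Appendix R 14.4.4.1 says that Table 14-1 "shows the assumed control clinical benefit rates for each group", and SAP 10.4.1 says the same of its own table: "Table 1 shows the assumed control clinical benefit rates for each group". Both list lung (labelled LSCL) 0.45, bladder 0.47, breast 0.50, colorectal 0.38, GIST 0.50, HNSCC 0.45, ovarian 0.47 and sarcoma 0.40. The Appendix R introduction explains that "this document outlines the design and analysis approach based on 8 example tumor cohorts".

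There is a rule for extra cohorts. In Appendix R 14.1.1.2 and SAP 10.1.2, besides enough enrolment, "the sponsor must have a reasonable estimate of the control clinical benefit rate". Section 10 words the matching rule more narrowly: "a decision will only be made for a group other than the 6 listed if" enrolment is sufficient and a rate estimate is available.

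**The concern.** R_g is the null value of the primary test and enters the model as an offset, θ_g = logit(π_g) − logit(R_g). For two of the six named cohorts the plan points to a table that does not contain it. The extra-cohort rule sets a condition but gives no value, source or date, and Section 10 applies it only outside the six, as though the six already had rates.

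The study is open-label and single-arm, with no data monitoring committee. The Amendment 2 rationale itself says that inference in such a trial depends heavily on the historical rate. Amendment 3 reopened these cohorts after responses had been seen among the six tumour types. Unless the two rates were fixed in an earlier record, they could be chosen with results in view. Because θ_g is borrowed across cohorts, a missing rate can also affect cohorts that do have one.

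**Working it through.** **Row check.** Squamous NSCLC is covered only if the general lung row is meant to apply to it. Ovarian (0.47), HNSCC (0.45) and bladder (0.47) have rows. Glioblastoma and cholangiocarcinoma have none in either table.

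**Reproducing the plan's own figures.** At an expected accrual of 10 per cohort, Table 14-2 averages over its eight cohorts to 0.144 (Null) and 0.920 (Alternative); at 5 per cohort, 0.144 and 0.812. The Appendix R model was re-simulated with Poisson accrual capped at 30, final look only, 600 trials per scenario, and 1.82 read as the prior SD of μ:

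| Accrual | Table 14-2 Null / Alt | Rerun, 0.80 rule | Rerun, 0.90 rule |
|---|---|---|---|
| 10 | 0.144 / 0.920 | 0.141 / 0.928 | 0.054 / 0.840 |
| 5 | 0.144 / 0.812 | 0.158 / 0.804 | 0.062 / 0.631 |

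The model is reproduced to within 2 percentage points. The published figures belong to the 0.80 rule of Appendix R 14.1.1.1 and 14.3.3.3, not the 0.90 rule of Protocol 10.4.2, 10.4.3 and the SAP.

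**Effect of the missing R_g.** Model: all 203 partitions of six cohorts, each weighted by 2^K × Π(n_k − 1)! (K clusters of sizes n_k, α = 2) times the product of the cluster marginal likelihoods. Within a cluster θ_g ~ N(μ, τ²), with μ ~ N(0, variance 1.82) and τ² ~ IG(3, 0.5), integrated numerically. If the variance is 1.8² instead, the 6/10 and 7/10 values move by at most 0.003.

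Assumed data (the plan gives none): the four listed cohorts at 4, 5, 4 and 5 of 10 with their tabulated rates, one unlisted cohort at 5/10, and the other as shown. Both unlisted cohorts share the same R_g.

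| Result | R_g 0.30 | 0.38 | 0.45 | 0.50 |
|---|---|---|---|---|
| 2/10 | 0.322 | 0.189 | 0.106 | 0.066 |
| 6/10 | 0.942 | 0.864 | 0.761 | 0.671 |
| 7/10 | 0.982 | 0.945 | 0.886 | 0.825 |
| 8/10 | 0.996 | 0.984 | 0.958 | 0.927 |
| 9/15 | 0.979 | 0.923 | 0.825 | 0.724 |
| 16/30 | 0.992 | 0.936 | 0.788 | 0.616 |

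Within 0.38 to 0.50:

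- 7/10 goes from success to promising, and 6/10 from promising to neither.
- 9/15 and 16/30 go from success to neither.
- 2/10 goes from continue to futility.

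Over six configurations of the other cohorts (listed four at 4 to 5 of 10, other unlisted at 4 or 5 of 10), 7/10 ranges over 0.92–0.96 at 0.38 and 0.78–0.86 at 0.50: success in all six, then in none.

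**Check without borrowing.** With a Beta(1,1) prior, Pr(π > R_g) is the upper tail of Beta(1 + y, 1 + n − y). For 6/10 it is 0.923, 0.826 and 0.726 at R_g 0.38, 0.45 and 0.50: success, promising, neither. The minimum success counts at those rates are 9, 10 and 11 of 15, and 15, 18 and 19 of 30.

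**Effect on a listed cohort.** With HNSCC at 7/10, NSCLC 4, bladder 4, ovarian 5 and both unlisted at 5/10, the HNSCC posterior falls from 0.904 to 0.874 as the missing R_g goes from 0.38 to 0.50. This crosses 0.90.

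**The case against.** The best defence is that Appendix R is a generic framework for all modules. Its eight cohorts are called examples, its table is titled as simulation input, and a cohort outside the list may enter once an estimate exists. On that reading glioblastoma and cholangiocarcinoma come in by the extra-cohort route, and the sponsor may hold the rates elsewhere. This explains how the gap arose but does not fill it. Section 10.4.3 cites the example table as the operative source, the route fixes no number, and Section 10 limits it to groups outside the six, so the two texts also conflict.

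A second objection is about size, and part of it stands:

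- Within 0.38 to 0.50 and at 10 patients, the success count moves only from 7 to 8 and the futility count from 1 to 2. In the tabulated configuration no 10-patient result passes through all three categories. That takes a larger cohort, or weaker results elsewhere (listed four and other unlisted all at 4/10: 7/10 goes from 0.924 to 0.774).
- The effect on listed cohorts matters only near 0.90. With all four listed at 6/10 and both unlisted at 5/10, HNSCC goes from 0.877 to 0.840 and is never a success within the span.

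The squamous NSCLC label is probably a slip and needs only confirmation.

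**Conclusion.** The concern holds. Two of the six primary decisions cannot be computed from the protocol and SAP, because the null value is absent from the table named as its source and from everywhere else. If the true rates lie within 0.38 to 0.50, the choice is worth one responder at 10 patients and can move a 15- or 30-patient cohort from success to neither. Rates below that span matter more: 6/10 is a success at 0.30 (0.942) and neither at 0.50. These sizes rest on assumed counts and rates; the absence of the rates does not.

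Separately, Table 14-2 and SAP Table 2 describe a success rule that Section 10.4 and the SAP do not use, on a cohort set that is not this trial's. A lesser wording point: Protocol 10.8 and SAP 9 describe the alternative as having effects that vary by group, yet all eight odds ratios lie between (0.71/0.29)/(0.45/0.55) = 2.99 and (0.73/0.27)/(0.47/0.53) = 3.05.

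**What to change.** 1. Add R_g for glioblastoma and cholangiocarcinoma, each with source and date, to Table 14-1 and SAP Table 1. Confirm which rate applies to squamous NSCLC. Do this before the next CBR analysis and without reference to those cohorts' results, or cite the earlier record if the rates were already fixed.
2. Report the two cohorts' posteriors over a stated range of R_g. If a rate was set after responses were known, label that cohort's decision exploratory.
3. Separately, rerun the simulation at the 0.90 rule for the cohorts that will be analysed (the six, plus any earlier cohort meeting minimum enrolment) and restate power and type I error.
4. In Protocol 10.8 and SAP 9, replace the statement about varying effects with a pointer to the Half and Two scenarios.

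The first step costs two sourced rates, one confirmation and two table edits, with no loss of power. The rerun will show lower power because of the threshold, not because of the added rates. With six cohorts of 10, odds ratio 3 in all, final look only and 1000 trials, power is about 0.90 at the 0.80 rule, against 0.79 at the 0.90 rule if the two rates are 0.30, or 0.83 if they are 0.45. The null success rate falls from about 0.15 to 0.06.
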